12.2 Adjustment for Covariates

The corresponding baseline value will be included as a covariate for the analysis of HAMD-17 and SDS mean scores using the mixed model for repeated measures (MMRM) as described in Sections 13.1 and 13.2.

12.3 Handling of Missing Data

The primary analyses of the primary and key secondary efficacy endpoints will be performed in 2 steps and the missing data issue is only involved in Step 1:

1. Data from Stages 1 and 2 will be analyzed separately assuming missing at random (MAR) using the stage-specific, direct likelihood-based MMRMs and scores that are missing, after any imputation of individual missing items as described in Sections 5.2.1 and 5.2.2, will not be imputed. The MMRM method is unbiased under the MAR assumption and can be thought of as aiming to estimate the treatment effect that would have been observed if all subjects had continued on treatment for the full study duration (EMA, 2009).
2. Weighted combination of statistics from the stage-specific MMRMs will be used to perform the hypothesis testing.

12.4 Multiple Comparisons / Multiplicity

The hypothesis testing for the primary and key secondary efficacy endpoints will be performed in a sequential order. That is, if there is no evidence to show the superiority of the pimavanserin treatment to the placebo with respect to the primary efficacy endpoint at the two-sided significance level of 0.05, no further testing for the key secondary efficacy endpoint will be performed. Thus, there is no need to adjust the alpha for the two comparisons between the 2 treatment groups and the family-wise Type I error rate is controlled strongly for the hypothesis testing for the primary and key secondary efficacy endpoints. Unadjusted p-values will be reported and the testing sequence will be used to determine statistical significance.

12.5 Examination of Subgroups

Treatment effect will be examined with respect to the primary and key secondary efficacy endpoints within the subgroups of sex (male and female), race (white and non-white), age (18-40 years and > 40 years), and the severity of depression at Baseline (Baseline HAMD-17 total score < 24 and \geq 24).

13. METHODS OF EFFICACY ANALYSES

13.1 Primary Efficacy Analysis

13.1.1 Primary Analysis

The primary efficacy endpoint is the change from Baseline to Week 5 in the Hamilton Depression Scale (17 Items) (HAMD-17) total score.

Let Δ_1 and Δ_2 be the difference in the mean change from Baseline to Week 5 in the HAMD-17 total score between the pimavanserin and placebo groups in Stage 1 and Stage 2 respectively. Let w be the weight for Stage 1 and $1-w$ the weight for Stage 2.

The null hypothesis is: $w\Delta_1 + (1 - w)\Delta_2 = 0$.

The alternative hypothesis is: $w\Delta_1 + (1 - w)\Delta_2 \neq 0$.

The hypothesis testing will be performed using the weighted combination of statistics from the stage-specific MMRM. The MMRMs will include effects for treatment group, visit, treatment-by-visit interaction, Baseline HAMD-17 total score, and the Baseline HAMD-17 total score-by-visit interaction. An unstructured covariance matrix will be used and the Kenward-Roger approximation will be used to adjust the denominator degrees of freedom.

[REDACTED]

In the event that the model fails to converge using the unstructured covariance matrix, the following covariance structures will be modeled in the order given (i.e. from least parsimonious to most parsimonious): heterogeneous Toeplitz, heterogeneous compound symmetry, heterogeneous autoregressive(1), Toeplitz, compound symmetry, autoregressive(1), variance components. The first covariance structure that allows for convergence will be selected for the final model.

Statistical Analysis Plan
2018

21 August

The overall treatment effect will be assessed as the weighted differences between the pimavanserin and placebo groups in least-squares mean change from Baseline to Week 5. The prespecified weight w , is 0.5/0.5 for Stage 1/Stage 2.

Inference will be conducted using the following weighted linear combination of stage-wise treatment effects (Chen et al., 2011 and Fava et al., 2003):

$$Z = \frac{w\hat{\Delta}_1 + (1-w)\hat{\Delta}_2}{\sqrt{w^2\text{Var}(\hat{\Delta}_1) + (1-w)^2\text{Var}(\hat{\Delta}_2)}} \sim N(0, 1) \quad (1)$$

In the above formula, $w = 0.5$ and $\hat{\Delta}_1$ and $\hat{\Delta}_2$ are the differences in least squares (LS) means between pimavanserin and placebo at Week 5, for Stages 1 and 2, respectively.

Summary statistics for the HAMD-17 total score (observed and change from Baseline), LS means, the between-group difference in LS mean with the corresponding 95% confidence interval, p-value, and the effect size (Cohen's d) will be presented at each post-Baseline visit for FAS1 and FAS2.

The treatment effect size (Cohen's d) is calculated using the following formula:

$$\text{Effect Size} = \text{LS mean difference} / \text{SD} \quad (2)$$

SD is the model-based estimate, i.e., the estimated standard deviation from the unstructured covariance matrix. The sign (+ or -) of the effect size will be chosen so that a positive value favors pimavanserin.

LS mean \pm SE from the MMRM models over time for the change from Baseline values by treatment group will be displayed in line plots for FAS1 in Stage 1 and FAS2 in Stage 2.

The weighted treatment differences in LS means between pimavanserin and placebo, the corresponding 95% CI, and the p-value will be presented at Week 5.

13.1.2 Sensitivity Analyses

The following 2 sensitivity analyses of HAMD-17 total score are planned.

1. Per-protocol Analysis

A sensitivity analysis similar to the primary analysis will be performed for PAS1 and PAS2.

2. Pattern-Mixture Models Assuming Missing Not At Random (MNAR)

Statistical Analysis Plan
2018

21 August

The sensitivity analysis is implemented using multiple imputations that are based on the distribution of placebo group responses over time. The underlying assumption is that subjects with missing data follow the distribution of the placebo responses. The following 3 steps are involved for both FAS1 and FAS2 separately:

- The posterior mean and covariance estimates from the SAS MI procedure using the available non-missing placebo data and random number seeds of 1030421 for Stage 1 and 103042 for Stage 2 will be utilized to impute missing data in the HAMD-17 total score. The imputed values will be constrained to be within the range of 0 to 52. [REDACTED]

[REDACTED]

- The change from Baseline to Week 5 in the HAMD-17 total score will then be calculated and analyzed for each of the 100 fully imputed datasets using an ANCOVA model with treatment group as a factor and the Baseline value as a covariate.
- The treatment LSMEAN differences will be averaged and the associated standard errors will be summarized based on within-imputation and between-imputation variance using the SAS MIANALYZE procedure, to yield a combined estimate for treatment effect with its associated 95% CI and p-value.

Inference will be made using the weighted linear combination of stage-wise, combined estimates for treatment effect using Equation (1).

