3.5 Determination of Sample Size

The primary efficacy endpoint is the change from Baseline to Week 5 in the Hamilton Depression Scale (17 Items) (HAMD-17) total score. For Stage 1, Baseline is Study Week 0 and Week 5 is Study Week 5. For Stage 2, Baseline is Study Week 5 and Week 5 is Study Week 10.

A total sample size of 168 evaluable subjects is estimated to provide at least 80% power at a two-sided significance level of 0.05 assuming a mean change in the HAMD-17 total score of -7.8 (SD=8) and -10 (SD=8) in Stage 1, and -2.8 (SD=6) and -6.0 (SD=6) in Stage 2 for the placebo and pimavanserin groups, respectively.

For the above calculation, the weight for each double-blind treatment stage is equal to 0.5 and it is assumed that approximately 70% of placebo subjects will be non-responders at the end of Stage 1.

Adjusting for a potential non-evaluable rate of up to 10%, approximately 188 subjects will be randomized into Stage 1 (47 to pimavanserin and 141 to placebo). It is anticipated that approximately 98 subjects will be randomized into Stage 2 (49 to pimavanserin and 49 to placebo).

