4. ANALYSIS SETS

Randomized Analysis Sets

Randomized Analysis Set for Stage 1 – The Randomized Analysis Set for Stage 1 (RAS1) will consist of all subjects who were randomized into Stage 1.

Randomized Analysis Set for Stage 2 – The Randomized Analysis Set for Stage 2 (RAS2) will consist of all subjects who were placebo non-responders from Stage 1 and who were randomized into Stage 2.

Subjects will be classified according to the randomized treatment assignment.

Safety Analysis Sets

Safety Analysis Set for Stage 1 – The Safety Analysis Set for Stage 1 (SAS1) will consist of all subjects who were randomized into Stage 1 and received at least one dose of study drug in Stage 1.

Safety Analysis Set for Stage 2 – The Safety Analysis Set for Stage 2 (SAS2) will consist of all subjects who were placebo non-responders from Stage 1, were randomized into Stage 2, and received at least one dose of study drug in Stage 2.

Subjects will be classified according to the actual treatment received.

Full Analysis Sets

Full Analysis Set for Stage 1 – The Full Analysis Set for Stage 1 (FAS1) will consist of all subjects who were randomized into Stage 1, received at least one dose of study drug in Stage 1, and have both a Baseline (Study Week 0) value and at least one post-Baseline value for the HAMD-17 total score in Stage 1.

Full Analysis Set for Stage 2 – The Full Analysis Set for Stage 2 (FAS2) will consist of all subjects who were placebo non-responders from Stage 1, were randomized into Stage 2, received at least one dose of study drug in Stage 2, and have both a Baseline (Study Week 5) value and at least one post-Baseline value for the HAMD-17 total score in Stage 2.

Subjects will be classified according to the randomized treatment assignment.

Per-protocol Analysis Sets

Per-protocol Analysis Set for Stage 1 – The Per-protocol Analysis Set for Stage 1 (PAS1) will consist of a subset of subjects in FAS1 who do not have any protocol deviation which is considered to have substantial impact on the primary efficacy outcome. The precise reasons

Statistical Analysis Plan
2018

21 August

for excluding subjects from PAS1 will be fully defined and documented *a priori* before the clinical database lock.

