5.3.1 Unscheduled Assessments

Both Scheduled and Unscheduled assessments, including the assessments at early termination visits, will be used for planned timepoint analyses. All assessments will be presented in data listings.

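### The placebo-based MNAR analysis of HAMD-17 drops dosed subjects who have no post-Baseline rating, so it can overstate robustness

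*SAP*

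**What the plan says.** SAP 13.1.2 plans two sensitivity analyses of the HAMD-17 total score. The first repeats the primary analysis on the per-protocol sets, which are subsets of the full analysis sets. The second is a pattern-mixture analysis by multiple imputation from the placebo data, followed by ANCOVA in each of 100 completed data sets, MIANALYZE, and the weighted combination in Equation (1).

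The second analysis states its assumption as "The underlying assumption is that subjects with missing data follow the distribution of the placebo responses". On population it says "The following 3 steps are involved for both FAS1 and FAS2 separately".

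Under SAP section 4, members of FAS1 must "have both a Baseline (Study Week 0) value and at least one post-Baseline value for the HAMD-17 total score in Stage 1", and members of FAS2 must "have both a Baseline (Study Week 5) value and at least one post-Baseline value for the HAMD-17 total score in Stage 2". A subject who was randomised and dosed but never rated afterwards in that stage is therefore not in the data that are imputed.

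A wider set exists: "The Randomized Analysis Set for Stage 1 (RAS1) will consist of all subjects who were randomized into Stage 1", with RAS2 as its Stage 2 counterpart. No planned treatment comparison of HAMD-17 uses either one. Part of the imputation step in 13.1.2 is blacked out. That is not held against the plan, because the populations are named before it and the opening of SAP section 12 assigns all efficacy analyses to FAS1 and FAS2.

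**The concern.** Excluding never-rated subjects does little harm in the primary analysis. SAP 12.3 assumes missing at random there, and a subject with no outcome adds almost nothing to the MMRM likelihood.

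The sensitivity analysis has a different job, which is to replace that assumption with a less favourable one. A pimavanserin subject with no post-Baseline score has the most missing data of all, and under the stated assumption should be given placebo-like outcomes. Dropping that subject has the same effect on the estimate as crediting them with the average benefit of the retained pimavanserin subjects. For these subjects the analysis falls back on the assumption it is meant to test.

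At stake is whether a positive result could be called robust to MNAR when part of the missing data was never put to the test. Imputation is feasible: these subjects should have a stage Baseline HAMD-17, and re-randomised subjects also have Stage 1 scores.

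**Working it through.** **Inputs (SAP 3.5 unless stated).** Stage 1 difference 10 - 7.8 = 2.2, SD 8. Stage 2 difference 6.0 - 2.8 = 3.2, SD 6. Weight w = 0.5. Two-sided alpha 0.05. 168 evaluable subjects at 1:3, so 42 and 126. Placebo non-response 70%, so 0.70 × 126 = 88 in Stage 2, or 44 per arm. Randomised numbers are 47/141 and 49/49. Assumed, because the documents do not give it: d, the share of the pimavanserin arm with no post-Baseline HAMD-17, taken as equal in both stages.

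**Step 1: reproduce the planned power.** The plan says "A total sample size of 168 evaluable subjects is estimated to provide at least 80% power".
- Weighted effect: 0.5 × 2.2 + 0.5 × 3.2 = 2.70
- V1 = 64 × (1/42 + 1/126) = 2.032; V2 = 36 × (1/44 + 1/44) = 1.636
- SE = sqrt(0.25 × 2.032 + 0.25 × 1.636) = 0.958
- Z = 2.70 / 0.958 = 2.82; power = Φ(2.82 - 1.96) = 80.5%

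The stated figure is confirmed.

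**Step 2: keep the never-rated subjects and impute them from placebo.** A share (1-d) of the pimavanserin arm carries the effect and a share d carries none, so the expected weighted effect is 2.70 × (1-d). Relative to this, the FAS-based estimate is too large by 1/(1-d). The SE is held at 0.958.

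| d | Effect | Z | Chance of p<0.05 | FAS inflation |
|---|---|---|---|---|
| 0 | 2.70 | 2.82 | 80.5% | none |
| 1% | 2.67 | 2.79 | 79.7% | 1% |
| 2% | 2.65 | 2.76 | 78.9% | 2% |
| 5% | 2.57 | 2.68 | 76.4% | 5% |
| 10% | 2.43 | 2.54 | 71.8% | 11% |

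One subject is 1/47 = 2.1% of the Stage 1 pimavanserin arm or 1/49 = 2.0% of the Stage 2 arm.

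**Step 3: what it takes to lose significance.** With the SE fixed, Z shrinks by (1-d), so a FAS result reaches p = 0.05 when d = 1 - 1.960/z.
- FAS p = 0.04 (z = 2.054): d = 4.6%
- FAS p = 0.03 (z = 2.170): d = 9.7%
- FAS p = 0.02 (z = 2.326): d about 16%

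**Step 4: simulation check.** 2,000 trials per scenario, 47/141 and 49/49 randomised, never-rated subjects as the only missing data, 30 placebo-based imputations, ANCOVA, Rubin's rules, Baseline unrelated to outcome.

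| Excluded from FAS (Stage 1 pim/pbo; Stage 2 pim/pbo) | Effect, FAS vs all | p<0.05, FAS vs all | Significant FAS results lost |
|---|---|---|---|
| 1/3; 1/1 | -2.68 vs -2.63 | 83.0% vs 82.0% | 1.1% |
| 2/7; 2/2 | -2.67 vs -2.56 | 82.6% vs 80.8% | 2.1% |
| 5/14; 5/5 | -2.67 vs -2.39 | 79.0% vs 72.4% | 8.4% |
| 0/19; 0/10 | -2.76 vs -2.76 | 83.2% vs 83.1% | 0.5% |

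A second simulation assumed a Baseline SD of 4, a Baseline-change correlation of -0.3 and 40 imputations. At 10% per arm it gave -2.72 vs -2.44, with 84.3% vs 78.1% significant and an SE of 0.92 both ways, which supports holding the SE fixed in Step 2. Across the three calculations the loss at 10% is 6.2, 6.6 and 8.7 points.

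**The case against.** The strongest counter-case is that very few subjects can be affected. HAMD-17 is scheduled weekly from Week 1 (Protocol Table 2), the early-termination visit includes it (Protocol 6.5.12), and sites are asked to make every reasonable effort to complete that visit (6.5.14). SAP 5.3.1 adds "Both Scheduled and Unscheduled assessments, including the assessments at early termination visits, will be used for planned timepoint analyses", and the Week 1 window opens on Day 2. Someone who stops early but attends one termination visit is in the FAS and is imputed. In Stage 2, an excluded subject must have attended Week 5, been re-randomised and then never been rated again. This stands. It rules out the tempting inference that the earliest dropouts go untested as a class, and nothing in the documents shows that those left out stopped for intolerance.

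Second, SAP 3.5 introduces the larger sample with "Adjusting for a potential non-evaluable rate of up to 10" per cent. A reader might infer that the plan expects 10% of subjects to have no rating. It does not say so: this is a sample-size allowance with no reasons given. Nor do the Stage 2 numbers fit such a loss. The 49 per arm comes from 0.70 × 141 = 98.7, which assumes no loss before Week 5; a 10% loss would leave about 0.70 × 127 = 89. This also stands, so 10% serves only as an assumed upper bound. The smaller Stage 2 hardly changes the drop. With a further 10% lost there (40 per arm) the SE is 0.980, and the chance of p<0.05 goes from 78.6% to Φ(2.43/0.980 - 1.96) = 69.8%, or 8.8 points.

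Third, Protocol 9.3 assigns the FAS to all efficacy endpoints, and keeping the primary population isolates the effect of the missing-data assumption. SAP section 6 also lists every subject excluded from the full set, with reasons. Both are fair, but neither repairs the gap: following the protocol does not make the population match the stated assumption, and a listing does not show the effect on the estimate.

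**Conclusion.** The point holds as a conditional weakness. The FAS restriction means the MNAR analysis does not apply its own assumption to dosed subjects with no rating in the stage, and robustness can be overstated as a result. Two conditions are needed: a true benefit, and excluded subjects on pimavanserin.

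A reader might go further and conclude that robustness is overstated as a matter of fact. The documents do not support that. They give no count of such subjects, and with exclusions on placebo only there is nothing to correct. Nor is this the plan's only departure from missing at random: SAP 13.3 counts missing HAMD-17 scores as non-remission and non-response, and adds LOCF to the secondary ANCOVAs. It is the only MNAR analysis of the continuous primary endpoint.

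At 1 to 2% the change is negligible. At 10% the inflation is 11%, which matters for a FAS p-value of about 0.03 to 0.05 and not for one of 0.02. These sizes rest on the planning effects and SDs, on the same d in both stages, and on an even spread of losses over the arms. If an overall 10% fell mostly on pimavanserin, d would be higher: a simulated case with 9 of 47 and 10 of 49 excluded on pimavanserin gave -2.70 vs -2.16. Nothing in the documents suggests such an imbalance. The primary MMRM and its Type I error are unaffected.

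**What to change.** In SAP 13.1.2 item 2, replace FAS1 and FAS2 with all subjects randomised into the stage who took at least one dose in it and have a stage Baseline HAMD-17, analysed by randomised arm. Impute all their missing post-Baseline scores from the placebo model, then apply the same ANCOVA, MIANALYZE step and Equation (1). The FAS version may be kept alongside. Report by arm and stage how many subjects the FAS omits for lack of a post-Baseline HAMD-17.

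The cost is a few lines of SAP text, a wider input data set, minor extra programming, and a sensitivity estimate that may be slightly less favourable. No new data are collected, and the primary analysis, alpha and sample size stay as they are. If hardly anyone is affected, the two versions will agree and the robustness claim is better supported.

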13.2 Key Secondary Efficacy Analysis

The key secondary efficacy endpoint is the change from Baseline to Week 5 in the SDS mean score. The hypotheses, the primary analysis method, and the line plots for the key secondary efficacy endpoint are the same as the hypotheses, the primary analysis method, and line plots for the primary efficacy endpoint described in Section 13.1.1 but with SDS replacing HAMD-17. A per-protocol analysis similar to the primary analysis will be performed for PAS1 and PAS2.

13.3 Other Secondary Efficacy Analyses

ANCOVA analyses for the secondary efficacy endpoints in this section will be performed using (1) the observed values (i.e., missing data will not be imputed) and (2) the last observation carried forward (LOCF) method for missing data (Note: for subjects without post-Baseline values, the Baseline values will be carried forward).

Remission rate at the end of the two 5-week treatment periods

Remission is defined as a HAMD-17 total score less than or equal to 7. Missing HAMD-17 total scores will be considered as non-remissions and the subjects with missing HAMD-17 total scores will be included in the denominator of the remission rate.

The remission rate will be compared between the pimavanserin and placebo groups within each stage using Pearson's chi-square test.

Let n be the total number of subjects in FAS1, n_{1q} be the number of placebo subjects in FAS1, n_{1p} be the number of pimavanserin subjects in FAS1, n_{2q} be the number of placebo subjects in FAS2 (i.e., placebo non-responders in Stage 1, were randomized to the placebo group in Stage 2, received at least one dose of study drug in Stage 2, and have both a Baseline [Study Week 5] value and at least one post-Baseline value for the HAMD-17 total score in Stage 2), and n_{2p} be the number of pimavanserin subjects in FAS2 (i.e., placebo non-responders in Stage 1, were randomized to the pimavanserin group in Stage 2, received at least one dose of study drug in Stage 2, and have both a Baseline [Study Week 5] value and at least one post-Baseline value for the HAMD-17 total score in Stage 2).

Let r_{1q} be the number of placebo remission subjects in FAS1 in Stage 1, r_{1p} be the number of pimavanserin remission subjects in FAS1 in Stage 1, r_{2q} be the number of placebo remission subjects in FAS2 in Stage 2, and r_{2p} be the number of pimavanserin remission subjects in FAS2 in Stage 2.

Let $q_1 = r_{1q} / n_{1q}$ and $p_1 = r_{1p} / n_{1p}$ be placebo and pimavanserin remission rate in Stage 1. Let $q_2 = r_{2q} / n_{2q}$ and $p_2 = r_{2p} / n_{2p}$ be placebo and pimavanserin remission rate in Stage 2, among

Statistical Analysis Plan
2018

21 August

placebo non-responders in Stage 1. Let w be the weight for Stage 1 and $1-w$ be the weight for Stage 2 (Note: w is 0.5 for this study).

The null hypothesis is: $w (P_1 - Q_1) + (1 - w) (P_2 - Q_2) = 0$.

The alternative hypothesis is: $w (P_1 - Q_1) + (1 - w) (P_2 - Q_2) \neq 0$.

Inference will be made using the following weighted linear combination of stage-wise treatment effects:

$$Z = \frac{w(p_1 - q_1) + (1 - w)(p_2 - q_2)}{\sqrt{w^2 \text{Var}(p_1 - q_1) + (1 - w)^2 \text{Var}(p_2 - q_2)}} \sim N(0, 1),$$

$$\text{where, } \text{Var}(p_i - q_i) = \frac{p_i(1-p_i)}{n_{ip}} + \frac{q_i(1-q_i)}{n_{iq}}, \quad i = 1, 2. \quad (3)$$

Treatment response rate at the end of the two 5-week treatment periods

Treatment response is defined as a reduction from Baseline in HAMD-17 total score of 50% or more. The hypotheses and the analysis method for treatment response rate are the same as the hypotheses and the analysis method for the remission rate but with treatment response replacing remission.

Change from Baseline to Week 5 in CGI-S score

The change from Baseline to Week 5 in CGI-S score will be analyzed in a similar way as the primary analysis of the primary efficacy endpoint using the weighted linear combination test with the Baseline HAMD-17 total score replaced by the Baseline CGI-S score.

CGI-I score at Week 5

The CGI-I score will be analyzed in a similar way as the primary analysis of the primary efficacy endpoint using the weighted linear combination test. The differences are (1) the response is CGI-I score (as opposed to the change from Baseline in CGI-I score) and (2) the Baseline CGI-S score will be used as the covariate in the MMRM models.

The CGI-I data will also be dichotomized by combining “very much improved” and “much improved” into 1 category (“Improved”), and the remaining items into the other (“Not Improved”). For analysis purposes, missing CGI-I scores and CGI-I scores of 0 (“not assessed”) will be treated as “Not Improved”.

Statistical Analysis Plan
2018

21 August

The observed score and dichotomized data will be descriptively summarized by treatment group and visit. Treatment comparisons with respect to the dichotomized data within each stage for FAS1 and FAS2 will be performed using Pearson's chi-square test. No overall treatment comparisons combining Stages 1 and 2 will be made with respect to the dichotomized data.

Change from Baseline to Week 5 in SF-12 scores

The change from Baseline to Week 5 in the norm-based Aggregate Physical Score and the norm-based Aggregate Mental Score will be summarized by treatment group and analyzed within each stage for FAS1 and FAS2 using the analysis of covariance (ANCOVA) model with treatment group as a factor and the corresponding Baseline value as a covariate. The overall treatment effect combining the 2 stages will be tested in a similar way as the primary efficacy endpoint using the weighted linear combination test in Equation (1).

Change from Baseline to Week 5 in DAI-10 score

The change from Baseline to Week 5 in DAI-10 score will be analyzed in a similar way as the SF-12 scores are analyzed.

Change from Baseline to Week 5 in KSS score

The change from Baseline to Week 5 in the 9-point KSS scale score will be analyzed in a similar way as the primary analysis of the primary efficacy endpoint using the weighted linear combination test with the Baseline HAMD-17 total score replaced by the Baseline KSS score.

Change from Baseline to Week 5 in MGH-SFI score

The change from Baseline to Week 5 in MGH-SFI score will be analyzed in a similar way as the SF-12 scores are analyzed.

Change from Baseline to Week 5 in BIS-11 score

The change from Baseline to Week 5 in BIS-11 score will be analyzed in a similar way as the primary analysis of the primary efficacy endpoint using the weighted linear combination test with the Baseline HAMD-17 total score replaced by the Baseline BIS-11 score.

Change from Baseline to Week 5 in SIS score

The change from Baseline to Week 5 in SIS score will be analyzed in a similar way as the primary analysis of the primary efficacy endpoint using the weighted linear combination test with the Baseline HAMD-17 total score replaced by the Baseline SIS score.

